  - 4.2. Be receiving monotherapy treatment for depressive symptoms with one of the following SSRI/SNRI antidepressants, in any formulation: citalopram, duloxetine, escitalopram, fluvoxamine, fluoxetine, milnacipran, levomilnacipran, paroxetine, sertraline, venlafaxine, desvenlafaxine, vilazodone, or vortioxetine at a stable dose (at or above the minimum therapeutic dose level) for at least 4 weeks, and for no greater than 12 months, at screening. Modification of an effective preexisting therapy should not be made for the explicit purpose of entering a subject into the study.
5. Have a MADRS total score  $\geq 25$  (performed by independent, centralized remote raters) at screening and must not demonstrate a clinically significant improvement (ie, an improvement of  $> 20\%$  on their MADRS total score) from the screening to baseline visit.
6. Have a Body Mass Index (BMI) between 18 and 35  $\text{kg/m}^2$  inclusive (BMI =  $\text{weight}/\text{height}^2$ ).
7. Must be otherwise healthy on the basis of physical examination, medical history, vital signs, 12-lead ECG, and clinical laboratory tests performed at screening. If there are abnormalities, they must be consistent with the underlying illness in the study population. If the results of the clinical laboratory tests are outside the normal reference ranges, the subject may be included only if the investigator judges the abnormalities or deviations from normal to be not clinically significant or to be appropriate and reasonable for the population under study. This determination must be recorded in the subject's source documents and initialed by the investigator.
8. Be willing and able to adhere to the prohibitions and restrictions specified in this

protocol.

9. Must sign an informed consent form (ICF) indicating that he or she understands the purpose of and procedures required for the study including peripheral biomarkers research (ie, blood, saliva) and is willing to participate in the study.
10. Sign a separate ICF if he or she agrees to provide an optional DNA sample for research. Refusal to give consent for the optional DNA research sample does not exclude a subject from participation in the study.
11. Criterion deleted per Amendment 2
12. Criterion deleted per Amendment 2
13. A woman must agree not to donate eggs (ova, oocytes) for the purposes of assisted reproduction during the study and for a period of at least 1 month after receiving the last dose of study drug.

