6.2. Clinical Laboratory Tests

Descriptive statistics will be presented for thyroid-stimulating hormone (TSH) and free thyroxine (FT₄), as well as all chemistry (including the lipid panel), hematology (including hemoglobin A1c [HbA1c]), and urinalysis (pH and specific gravity) laboratory parameters at each scheduled time point. In addition, change from baseline to all postbaseline time points will be summarized for chemistry, hematology, urinalysis (pH and specific gravity), TSH, and FT₄ parameters and displayed by treatment group.

The number and percentage of subjects with treatment-emergent postbaseline markedly abnormal postbaseline values will be presented by treatment group. Clinical laboratory test values will be considered “treatment-emergent markedly abnormal” (TEMA) using the criteria defined by the sponsor listed in Attachment 4. The identification of TEMA laboratory values is based on the postbaseline value being out of range while the baseline value is either missing or within the range given in Attachment 4. If postbaseline laboratory results are above the upper limit and the baseline value is below the lower limit, then the postbaseline abnormality will also be considered TEMA. The same applies to the postbaseline value being below the lower limit with the baseline value being above the upper limit.

In addition, the number of subjects with the following shifts in chemistry laboratory values from baseline to the maximum postbaseline time point will be presented:

- Glucose:
 - from <100 mg/dL to ≥ 126 mg/dL (normal to high)
 - from <100 mg/dL to [≥ 100 mg/dL - <126 mg/dL] (normal to borderline high)
 - from [≥ 100 mg/dL - <126 mg/dL] to ≥ 126 mg/dL (borderline high to high)
- Triglycerides:
 - from <150 mg/dL to ≥ 200 mg/dL (normal to high/very high)
 - from <150 mg/dL to ≥ 500 mg/dL (normal to very high)
 - from [≥ 150 mg/dL - <200 mg/dL] to ≥ 200 mg/dL (borderline high to high/very high)
 - from [≥ 150 mg/dL - <200 mg/dL] to ≥ 500 mg/dL (borderline high to very high)
 - from [≥ 200 mg/dL - <500 mg/dL] to ≥ 500 mg/dL (high to very high)
- Total Cholesterol
 - from <200 mg/dL to ≥ 200 mg/dL (normal to borderline high/high)
 - from <200 mg/dL to ≥ 240 mg/dL (normal to high)
 - from <200 mg/dL to [≥ 200 mg/dL - <240 mg/dL] (normal to borderline high)
 - from [≥ 200 mg/dL - <240 mg/dL] to ≥ 240 mg/dL (borderline high to high)
- HDL Cholesterol: from ≥ 40 mg/dL to <40 mg/dL (normal to low).

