The following conversion rules will be used: Glucose 1 mg/dL=0.05551 mmol/L; Triglycerides 1 mg/dL=0.01129 mmol/L; Total Cholesterol, HDL Cholesterol 1 mg/dL=0.02586 mmol/L.

The incidence of subjects with treatment-emergent ALT values >3 *upper normal limit (ULN), AST > 3 *ULN, or total bilirubin >2 *ULN will be presented for the double-blind phase. Additionally, incidence of treatment-emergent hepatic toxicity (suspected Hy's Law⁴ cases) defined as (ALT values >3 *ULN or AST values > 3 *ULN) AND total bilirubin values >2 *ULN will be presented for the double-blind phase. Similar to the markedly abnormal analysis, only subjects with baseline (ALT values ≤ 3 *ULN or AST ≤ 3 *ULN) (AND baseline total bilirubin values ≤ 2 *ULN for hepatic toxicity) (or if baseline value is missing) will be eligible for these analyses.

A listing of subjects with markedly abnormal laboratory values will be provided.

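### The stand-alone treatment-emergent bilirubin row in SAP 6.2 has no bilirubin baseline condition, and the ALT/AST baseline wording can be read two ways

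*SAP*

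**What the plan says.** SAP 6.2 (Clinical Laboratory Tests) promises three single-analyte counts, introduced with "The incidence of subjects with treatment-emergent ALT values" and continuing to AST and total bilirubin. It adds a fourth output, "incidence of treatment-emergent hepatic toxicity", which is the suspected Hy's Law composite: ALT or AST above 3×ULN together with total bilirubin above 2×ULN.

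One sentence then sets eligibility for all four. It opens "Similar to the markedly abnormal analysis, only subjects with baseline" and gives the enzyme condition as ALT at or below 3×ULN *or* AST at or below 3×ULN: "only subjects with baseline (ALT values ≤ 3 *ULN or AST ≤ 3 *ULN". It attaches a baseline bilirubin limit of 2×ULN, and closes "for hepatic toxicity) (or if baseline value is missing) will be eligible for these analyses". The bilirubin limit is thus tied in words to the composite alone.

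The markedly abnormal rule that the sentence says it resembles appears earlier in the same section. It turns on "the postbaseline value being out of range while the baseline value is either missing or within the range given in Attachment 4", so each parameter is judged against its own baseline.

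On entry, Protocol 4.1 criterion 7 deals with laboratory results outside the reference range by judgement: "the subject may be included only if the investigator judges the abnormalities or deviations from normal to be not clinically significant", or if they are considered appropriate for the population. Protocol 4.2 criterion 1 excludes moderate to severe hepatic insufficiency by Child-Pugh score. Neither sets a numeric limit for ALT, AST or bilirubin.

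**The concern.** A treatment-emergent count should contain only abnormalities that were absent at baseline. The bilirubin row does not ensure this, because nothing in the sentence compares a subject's later bilirubin with that subject's own baseline bilirubin. The enzyme wording leaves the same doubt over the ALT and AST rows: one programmer could apply the shared *or* condition to every row, while another could apply each enzyme's limit to its own row.

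Liver tables in a trial of this size hold very few subjects and are read almost case by case. One long-standing elevation labelled as new gives one arm an apparent liver signal. One new rise filtered out hides a signal.

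**Working it through.** There is no sample-size, power or alpha figure to reproduce. The rule can be checked completely by enumeration.

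**Inputs.** The thresholds (3×ULN for each enzyme, 2×ULN for bilirubin) and the eligibility sentence come from SAP 6.2. The arm size of 50 comes from SAP 1.4 and Protocol 11.2.

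**Set-up.** Score ALT, AST and bilirubin at baseline as above or not above threshold, giving 2 × 2 × 2 = 8 baseline states. Each analyte is raised in 4 of them. Three rules are compared:

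1. *Literal*: every row requires baseline ALT ≤3×ULN or AST ≤3×ULN. The composite also requires bilirubin ≤2×ULN.
2. *Respectively*: the ALT row is filtered on baseline ALT and the AST row on baseline AST. The bilirubin row has no stated filter.
3. *Own baseline*: each single-analyte row is filtered on its own analyte, as in the markedly abnormal rule.

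**Unchanged abnormalities counted as treatment-emergent**

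| Row | Raised at baseline (states) | Literal | Respectively | Own baseline |
|---|---|---|---|---|
| ALT >3×ULN | 4 | 2 | 0 | 0 |
| AST >3×ULN | 4 | 2 | 0 | 0 |
| Bilirubin >2×ULN | 4 | 3 | 4 | 0 |

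The 2 states in the literal ALT row are those with AST not raised; for example, baseline ALT of 4×ULN and AST of 2×ULN passes the filter. The AST row mirrors this. The literal bilirubin row blocks only the state in which both enzymes are also raised.

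**New abnormalities lost.** Under the literal rule, a subject with normal baseline bilirubin but both enzymes above 3×ULN is ineligible, so a new bilirubin rise in that subject is dropped. Under the own-baseline rule no new single-analyte abnormality is lost.

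**Composite.** The full criterion is present at baseline in 3 states (bilirubin raised with ALT, AST or both). The stated bilirubin limit blocks all 3, so 0 of 3 unchanged composites are counted. In the other 8 − 3 = 5 states the criterion is not met at baseline. Each can move to 3 post-baseline states that meet it, giving 5 × 3 = 15 new-onset transitions.

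- The text as written excludes 6 of the 15: those starting from raised bilirubin alone (3), and those starting from both enzymes raised with normal bilirubin (3).
- Requiring all three analytes to be normal at baseline would exclude 12 of the 15 (4 starting states × 3).
- Counting whenever the criterion is met after baseline and was not met at baseline excludes none.

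These are counts of logical states, not of subjects, and they carry no probability.

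**Size per subject.** 1/50 = 0.02, or 2 percentage points of one arm's rate.

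**The case against.** The strongest reply is that the enzyme phrase is shorthand. The sentence governs separate ALT and AST rows, the rows are labelled treatment-emergent, and the opening words point to a rule that works parameter by parameter. Read as *respectively*, the ALT and AST rows miscount nothing. This is a plausible reading, so the enzyme part of the point stands only as an ambiguity. A reader might infer that the ALT and AST rows are definitely wrong; the text does not establish that. The reply does not help the bilirubin row, which goes from a filter on the wrong analytes to no filter.

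A second reply is that other outputs reveal baseline status. SAP 6.2 summarises change from baseline for chemistry parameters and lists markedly abnormal values. Protocol 11.8 adds a listing of results outside the reference range. A careful reader could spot a pre-existing elevation there. But the Attachment 4 limits are fixed values (ALT 200 U/L, AST 250 U/L, total bilirubin 3.0 mg/dL), not ULN multiples, and a listing does not correct the incidence count.

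A third reply is that entry screening makes such baselines unlikely in subjects required to be otherwise healthy. That is fair as to frequency. It does not make the number zero, because the criteria rely on judgement.

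**Conclusion.** The point holds as a minor correction to a safety-table definition. On either reading of *or*, the stand-alone bilirubin row can count an unchanged baseline bilirubin above 2×ULN as treatment-emergent, which departs from the own-baseline principle the sentence invokes. On the literal reading, the row also loses a new rise when both enzymes were raised at baseline, and the enzyme rows can count unchanged elevations.

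Two stronger inferences are not supported. First, a reader might conclude that the suspected Hy's Law count is inflated by cases fully present at baseline; the bilirubin limit already blocks these. A subject with one enzyme raised at baseline can enter that count only through a new bilirubin rise, and then the full criterion is first met on treatment. Second, a reader might conclude that the composite should require ALT, AST and bilirubin all to be normal at baseline. The event joins the enzyme and bilirubin parts with *and*, so its absence at baseline requires only that one part was not met. The stricter condition would remove a genuinely new case from the table.

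The number of subjects affected cannot be computed, since neither document gives baseline frequencies; zero is possible. The 2-point figure assumes about 50 treated subjects per arm. The primary and efficacy analyses are untouched.

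**What to change.** Replace the eligibility sentence in SAP 6.2 with one condition per row:

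- ALT row: baseline ALT ≤3×ULN, or missing.
- AST row: baseline AST ≤3×ULN, or missing.
- Bilirubin row: baseline total bilirubin ≤2×ULN, or missing.
- Hepatic-toxicity composite: treatment-emergent when the full criterion is met after baseline and was not met at baseline. State how a missing baseline component is handled; the present text allows missing baselines.

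Add a listing that flags every subject counted in the composite who had a component already raised at baseline, so that a reader can weigh those cases separately.

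The cost is a short SAP edit and one listing flag, with no new data. The trade-off is that a subject already above a single-analyte threshold who worsens further will not appear in that row; the change-from-baseline summaries and the existing laboratory listings remain the place to look for such a subject.

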6.2.1. Homeostatic Assessment (HOMA) Modeling

Insulin resistance and beta-cell function based upon fasting glucose and insulin using the homeostatic assessment (HOMA) [3] model will be assessed. Two variables, HOMA IR (insulin resistance) and HOMA-%B (beta-cell function) will be derived. The relationship between glucose and insulin secretion, mathematically approximated using a simple nonlinear solution, is given below:

$$\text{HOMA Insulin Resistance (IR)} = \frac{FI}{22.5e^{-\ln FG}}$$

$$\text{HOMA Beta Function (B)} = \frac{20 \times FI}{[FG - 3.5]}$$

where FG = fasting glucose (mmol/L); FI = fasting insulin (mU/L); Insulin:
1 μ IU/mL = 6.945 pmol/L. HOMA IR and HOMA-%B will not be derived if FG is \leq 3.5.

The descriptive statistics for HOMA-IR and HOMA-%B at baseline (DB) and end point (DB) for the safety analysis set will include the following:

Geometric mean (GM) = exp(mean(logs));

GM mean \pm 1 SD = (exp(mean(logs) - 1 SD(logs)), exp(mean(logs) + 1 SD(logs)));

where logs indicates the natural logarithm of the HOMA values.

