### **Safety Evaluations**

Standard safety evaluations including collection of AEs and concomitant medications, physical examination, body weight, waist circumference, vital signs, 12-lead ECG, urine drug test, alcohol breath test, pregnancy testing, and clinical laboratory tests will be performed to monitor subject safety throughout the study.

The homeostatic model assessment will be conducted to estimate changes in beta-cell function and insulin sensitivity. The model requires both glucose and insulin measurements. It is known that atypical antipsychotic medications, including quetiapine XR, may cause insulin resistance; at present, there is no evidence that JNJ-42847922 has any impact on glucose metabolism.

Emergence of suicidal ideation will be assessed using the C-SSRS. The C-SSRS has been used frequently in clinical studies and it is a standard measure for suicidal ideation assessment; its use is in accordance with Food and Drug Administration (FDA) guidance.

The effect on sexual functioning will be measured by the ASEX. The ASEX has shown satisfactory reliability and validity.

Drug-induced EPS will be monitored using the ESRS-A. The ESRS-A is an abbreviated manualized version of the ESRS, a semi-structured interview that rates parkinsonian symptoms, dystonia, dyskinesias, and akathisia over the previous 7 days. The ESRS-A is being included since the comparator medication, quetiapine XR, is an antipsychotic with the potential to cause EPS and akathisia.

In addition, potential withdrawal effects will be assessed by the clinician using the PWC. The PWC is a reliable and sensitive instrument for the assessment of discontinuation symptoms.

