### **Clinical Laboratory Tests**

Laboratory data will be summarized by type of laboratory test and treatment. Reference ranges and markedly abnormal results (specified in the SAP) will be used in the summary of laboratory data. Descriptive statistics will be calculated for each laboratory analyte at baseline and for observed values and changes from baseline at each scheduled time point. A listing of subjects with any laboratory results outside the reference ranges will be provided. A listing of subjects with any markedly abnormal laboratory results will also be provided.

The homeostatic model assessment will be conducted to estimate changes in beta-cell function and insulin sensitivity based on insulin and glucose laboratory values.

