1.1. Trial Objectives

Objectives	Endpoints
Primary	

 To assess, in subjects with major depressive disorder (MDD) who have had an inadequate response to current antidepressant therapy with a selective serotonin reuptake inhibitor (SSRI) or serotonin-norepinephrine reuptake inhibitor (SNRI), the efficacy of flexibly dosed JNJ-42847922 (20 mg or 40 mg) compared to flexibly dosed quetiapine extended-release (XR) (150 mg or 300 mg) as adjunctive therapy to an antidepressant drug in delaying time to all-cause discontinuation of study drug over a 6-month (24-week) treatment period. 	
 Time to all-cause discontinuation of study drug.
Secondary	

 To assess the efficacy of JNJ-42847922 compared to quetiapine XR in the adjunctive treatment of MDD based on: 
 Achieving and sustaining remission of depressive symptoms Achieving and sustaining response of depressive symptoms Improving depressive symptoms in subjects with significant insomnia versus those without significant insomnia 	
 The proportion of subjects achieving (at Week 12) and sustaining remission at Weeks 18 and 24. Remission is defined as Montgomery-Asberg Depression Rating Scale (MADRS) total score ≤ 12. The proportion of subjects achieving (at Week 12) and sustaining response at Weeks 18 and 24. Response is defined as $\geq 50\%$ improvement from baseline MADRS total score. Change from baseline to Weeks 12, 18, and 24 in the MADRS total score in subjects with significant insomnia (baseline Insomnia Severity Index [ISI] score ≥ 15) versus those without significant insomnia (baseline ISI

Objectives	Endpoints
	score <15).

 - Improving anxiety symptoms 	
 - Change from baseline to Weeks 12, 18, and 24 in the 14-item Hamilton Anxiety Rating Scale (HAM-A) total score.

 • To assess the effect of JNJ-42847922 compared to quetiapine XR as adjunctive therapy for MDD on metabolic parameters during long-term (6 months) treatment, including: 	

 - Weight 	
 • The proportion of subjects with weight gain $\geq 7\%$ of baseline body weight at end-of-study assessment.

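### HOMA is included to estimate change, but SAP 6.2.1 summarises only baseline and end-point levels and specifies no paired change from baseline

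*SAP*

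**What the plan says.** The protocol gives the purpose of HOMA twice. Section 3.2 (Safety Evaluations): "The homeostatic model assessment will be conducted to estimate changes in beta-cell function and insulin sensitivity". Section 11.8 (Clinical Laboratory Tests): "The homeostatic model assessment will be conducted to estimate changes in beta-cell function and insulin sensitivity based on insulin and glucose laboratory values". Section 3.2 also gives the reason: "It is known that atypical antipsychotic medications, including quetiapine XR, may cause insulin resistance". It adds that nothing so far suggests an effect of JNJ-42847922 on glucose metabolism.

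SAP 6.2.1 derives HOMA-IR and HOMA-%B from fasting glucose (FG, mmol/L) and fasting insulin (FI, mU/L). The planned output is: "The descriptive statistics for HOMA-IR and HOMA-%B at baseline (DB) and end point (DB) for the safety analysis set will include the following". The statistics listed are the geometric mean and the range from one SD below to one SD above it, computed on logs ("where logs indicates the natural logarithm of the HOMA values"). The section names no change, no ratio to baseline, no paired subset and no treatment group. It also has a missing-data rule, "HOMA IR and HOMA-%B will not be derived if FG is" at or below 3.5, which applies to both indices.

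SAP 6.2 does plan change from baseline, by treatment group, for the measured chemistry analytes, which include glucose and insulin. It does not name the derived HOMA variables.

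**The concern.** The quantity the protocol asks for is a change, and the SAP specifies two separate cross-sections. A reader of the resulting table would have to form the change by dividing one geometric mean by the other. That can mislead in two ways. The two means may come from different subjects, so the ratio may reflect who supplied a later sample. And the SDs at the two visits do not give the SD of the change, so the ratio has no standard error or interval. The SAP specifies change from baseline for the laboratory analytes, vital signs, weight, ECG and ASEX. HOMA, which the protocol describes by its change, is the exception.

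At stake is the readability of one metabolic safety summary in a trial whose comparator is expected to affect insulin resistance. The primary analysis is not touched.

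**Working it through.** The plan states no figure for HOMA (no SD, correlation or power), so there is nothing to reproduce. The check is textual, with illustrative arithmetic.

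**1. When the planned table gives the change.** Let B and E be a subject's HOMA value at baseline and End point (DB). If the same n subjects supply both, mean(log E) − mean(log B) = mean(log E − log B). The ratio of geometric means is then exactly the geometric mean change ratio.

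**2. When it does not.** Invented example: baseline values 1, 1, 1, 4, 4, 4, with end-point values 1, 1, 1 from the first three subjects only.
- Baseline geometric mean = exp[(3·ln 1 + 3·ln 4)/6] = 2.0
- End-point geometric mean = 1.0
- Ratio from the table = 0.5, an apparent halving
- Paired ratio in the three subjects with both values = 1.0

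**3. Can the two sets differ here?** Yes, by an amount the documents do not give.
- SAP 2.8 defines End point (DB) as the last post-baseline result in the double-blind phase. The Time and Events Schedule has the first on-treatment chemistry at Week 6, so a subject who leaves earlier may have none.
- Early withdrawers have chemistry scheduled at the end-of-study visit (footnote s). SAP Table 1 has no follow-up row for chemistry, and SAP 2.2 runs the double-blind phase to the later of the last double-blind visit and the withdrawal date. Whether such a sample counts is not settled.
- The FG rule can remove a subject at one time point only.
- The sample-size section assumes 50% discontinuation on quetiapine XR. With hazard ratio 0.415, this implies 1 − 0.5^0.415 = 25% on JNJ-42847922. These are 24-week totals. Only subjects who leave with no usable post-baseline sample matter, and they are a smaller, unknown number.

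**4. Precision cannot be recovered.** With log-SD s at both visits and within-subject correlation r, SD(log change) = s·√[2(1 − r)]. Take s = 0.5 (assumed):
- r = 0.3: 0.5·√1.4 = 0.59
- r = 0.9: 0.5·√0.2 = 0.22

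The planned tables would be identical in both cases, because r is not reported.

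**5. What a paired summary would give.** Assumed inputs: s = 0.5 to 0.7, r = 0.3 to 0.9, n = 35 to 50 per arm with both values. The 80% interval uses z = 1.2816.

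| Quantity | Factor | s=0.5, r=0.9, n=50 | s=0.7, r=0.3, n=35 |
|---|---|---|---|
| Ratio to baseline within an arm | exp[1.2816·s·√(2(1−r)/n)] | ×/÷ 1.04 | ×/÷ 1.20 |
| Between-arm ratio, change only | exp[1.2816·s·√(2(1−r))·√(2/n)] | ×/÷ 1.06 | ×/÷ 1.29 |
| Between-arm ratio, adjusted for log baseline | exp[1.2816·s·√(1−r²)·√(2/n)] | ×/÷ 1.06 | ×/÷ 1.23 |

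**6. The FG rule.** HOMA-IR = FI/(22.5·e^(−ln FG)) = FI·FG/22.5. With FI = 10 and FG = 5, both forms give 2.222. With FI = 10 and FG = 3.5, HOMA-IR is 35/22.5 = 1.56, an ordinary value. HOMA-%B = 20·FI/(FG − 3.5) has a zero denominator at that point. Only HOMA-%B needs the exclusion.

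**The case against.** The best defence is that this is a supplementary summary in a descriptive safety section. Much of the defence stands.

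- The metabolic objective ("To assess the effect of JNJ-42847922 compared to quetiapine XR as adjunctive therapy for MDD on metabolic parameters during long-term (6 months) treatment") lists weight gain, triglyceride shifts and fasting-glucose shifts as its endpoints. HOMA is not among them. A reader might infer that the SAP fails a stated secondary objective or drops a promised between-drug HOMA comparison. The documents support neither: the protocol promises changes, and the interest in a contrast comes only from its rationale.
- Changes in glucose and insulin are already summarised by treatment group at every post-baseline time point, so metabolic effects are not left unexamined and the Week 6 and Week 12 samples are used. The gap remains, because separate mean changes in the two inputs do not determine the change in a nonlinear function of both.
- SAP Section 6 refers safety analyses to actual treatment received, so display by arm is probably intended, and the wording of 6.2.1 does not forbid further statistics. But a statistic that is not written down is not pre-specified.
- End point (DB) takes the last available result, including unscheduled ones, so anyone who leaves after Week 6 can contribute. The mismatch between the two sets may be small. The SAP could have required pairing and does not.
- The FG rule probably affects few samples: 3.5 mmol/L is 3.5/0.05551 = 63 mg/dL, in subjects who must be otherwise healthy. Keeping both indices on the same samples is a defensible choice.

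**Conclusion.** The point holds as a specification gap of minor to modest size. The protocol says HOMA is done to estimate changes, while SAP 6.2.1 specifies no change, no common set of subjects and no treatment grouping. The change can be read from the planned table only if the same subjects supply both values, and even then without precision.

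A reader might go further and say that the plan cannot deliver the change at all, or that baseline imbalance would confound the arms. The first is too strong, because the ratio of geometric means is exact in a paired set. The second is wrong, because chance imbalance between randomised arms adds noise and is not confounding.

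The example with mismatched subjects is invented, and every interval width above rests on assumed SDs, correlations and sample sizes. They illustrate what a paired summary would show and do not measure a bias in this trial. Any precision gained by baseline adjustment is likewise illustrative.

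**What to change.** In SAP 6.2.1:

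1. For subjects with both a baseline and an End point (DB) value, summarise log(end point/baseline) for HOMA-IR and HOMA-%B by treatment group. Report the number of pairs and the geometric mean ratio with its 80% CI (the level used in the SAP's efficacy sections).
2. Give the between-arm ratio with an 80% CI from an ANCOVA on the log change, with treatment, baseline insomnia status and log baseline HOMA. Label it descriptive. No test is needed, and a repeated-measures model is not required.
3. Apply the exclusion at FG ≤ 3.5 mmol/L to HOMA-%B only (minor).

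The cost is one extra table and a few lines of SAP text. No new samples or visits are needed.
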